8.1.6. Pregnancy

A female participant must be discontinued from study treatment if a positive serum pregnancy test is obtained.

8.1.7. Temporary Discontinuation

A participant may be withdrawn from study treatment as discussed in Section 8.1 but continue in the follow-up period of the study for collection of efficacy and safety data.

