7.6. Treatment Compliance

7.6.1. 12-Week Double-Blind Treatment Period

- During study Visit 2 (Randomization Visit/Day 1) through Visit 6 (Day 84) during the 12-week Treatment Period, when participants are dosed at the site, they will receive study treatment directly from the investigator or designee, under medical supervision. The date and time of each dose administered in the clinic will be documented in the eCRF for all participants. For countries where the clip-on Propeller Sensor for ELLIPTA is available, date and time of each dose administered in the clinic will also be captured via the Sensor.
- Between study visits during the 12-week Treatment Period, when participants self-administer study treatment at home, compliance with double-blind study treatment will be assessed by the study site staff by reviewing the dose counter on the ELLIPTA during the inhaler dispensing and return visits and by recording the compliance in the eCRF. For countries where the clip-on Propeller Sensor for ELLIPTA is available, compliance will also be captured via the Sensor.
- A record of the number of ELLIPTA inhalers dispensed to and taken by each participant must be maintained and reconciled with study treatment and compliance records. Treatment start and stop dates, including dates for treatment delays will also be recorded in the eCRF.

Participant compliance with double-blind study treatment will be assessed at Visits 3 through 6, by reviewing the clip-on Propeller Sensor for ELLIPTA data (for countries where the Propeller Sensor for ELLIPTA is available) or by reviewing the dose counter on the ELLIPTA (countries where the Propeller Sensor for ELLIPTA is not available). Participants must be $\geq 80\%$ to $\leq 120\%$ compliant in taking study treatment between-on-treatment visits. Participants who fall outside this range should be re-educated on treatment compliance by their site. This re-education should be documented in the participant's source document. If the double-blind study treatment is prematurely discontinued during the 12-Week Double-Blind Treatment Period or study treatment

compliance repeatedly falls outside of acceptable ranges, the study sponsor/site monitor must be contacted to discuss participant eligibility for continued participation in the study.

7.6.2. 12-Week Post-Treatment Follow-up Period

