8.1. Discontinuation of Study Treatment

A participant may be discontinued from study treatment but continue in the study for collection of data (including efficacy and safety data) and to minimize missing data. Participants who discontinue from study treatment will move directly into the 12-Week Post Treatment Follow Up Period starting with Visit 7, 28 days following the discontinuation date.

[figure not shown]
If a higher than expected number of participants prematurely discontinues double-blind study treatment or prematurely discontinues from the study, additional participants may be randomized, at the discretion of the Sponsor.

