8.1.8. Rechallenge

8.1.8.1. Study Treatment Restart or Rechallenge

Study treatment restart or rechallenge after liver chemistry stopping criteria are met by any participant in this study is not allowed.

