8.2. Withdrawal from the Study

A participant may withdraw from the study at any time during the study (including the Screening Period, the 12-Week Double-Blind Treatment Period or the 12-Week Post-Treatment Follow-Up Period) at his/her own request, or may be withdrawn at any time at the discretion of the investigator for safety, behavioral, compliance or administrative reasons.

If a higher than expected number of participants prematurely discontinues double-blind study treatment or prematurely discontinues from the study, additional participants may be randomized, at the discretion of the Sponsor.

If the participant withdraws consent for disclosure of future information, the sponsor may retain and continue to use any data collected before such a withdrawal of consent.

If a participant withdraws from the study, he/she may request destruction of any samples taken and not tested, and the investigator must document this in the site study records.

Refer to the SoA (Section 2) for data to be collected at the time of study withdrawal and follow-up and for any further evaluations that need to be completed.

Treatment failure or recurrent exacerbation does not mandate withdrawal from the study, unless there is a safety concern as judged by the Investigator, in consultation with the Medical Monitor if necessary.

The primary reason for subject withdrawal will be recorded in the eCRF. Primary reasons for withdrawal will be categorized as:

- adverse event
- withdrew consent
- lost to follow-up
- protocol deviation
- lack of efficacy
- subject reached protocol-defined stopping criteria
- study closed/terminated
- investigator discretion

Specific regard should be given to distinguishing withdrawals due to an adverse event, lack of efficacy and protocol deviation. Participant compliance with study treatment during the 12-Week Double-Blind Treatment Period will be assessed as described in Section 7.6.1.

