9.3. Treatment of Overdose

An overdose is defined as a dose greater than the doses described in Section 7.1 which results in clinical signs and symptoms. In event of an overdose the participants should be closely monitored for AEs/SAEs and these should be recorded in the eCRF.

GSK does not recommend specific treatment for an overdose for nemiralisib.

Decisions regarding treating the overdose, and dose interruptions or modifications will be made by the investigator in consultation with the Medical Monitor based on the clinical evaluation of the participant.

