Secondary	
The key secondary endpoint of number of exacerbations (moderate and severe) over the 12-Week treatment period will be analysed using a Bayesian generalized linear model assuming a negative binomial distribution for the underlying exacerbation rate with a log link and an offset to account for the length of time in study for each participant. Non-informative priors will be used for all modelling assumptions. The exacerbation rates for the selected nemiralisib dose and placebo arms, along with the ratio in exacerbation rates nemiralisib/placebo, will be estimated and corresponding 95% credible intervals produced.

Exploratory	Will be described in the RAP

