12.9.5. Treatment of COPD Exacerbations

To be eligible for this protocol, at Visit 1 (Screening), participants must present with a moderate or severe (requires hospitalization) acute exacerbation of COPD requiring treatment with SoC (defined for this protocol as treatment with oral/systemic corticosteroid[s] **and** antibiotic[s]) to be confirmed by an experienced physician (referred to as the ‘index COPD exacerbation;’ See Inclusion Criterion 4). SoC must be documented in the participant’s source documentation and in the eCRF.

For the index COPD exacerbation at Screening and any subsequent COPD exacerbation(s) during the study (Screening, 12-Week Double-Blind Treatment Period, and the 12-Week Post-Treatment Follow-Up Period), the Investigator/medically qualified health care personnel should treat the participant’s COPD exacerbation as deemed medically appropriate. If medically necessary, the Principal Investigator or other medically qualified health care personnel may stop the participant’s double-blind study treatment temporarily in order to treat the COPD exacerbation.

All medications (COPD and non-COPD) used for the treatment of an exacerbation(s) must be recorded in the source documents and in the COPD Exacerbation form in the eCRF.

12.9.6. Guidelines for Distinguishing Between Continuation of an Existing Exacerbation versus a Subsequent New Exacerbation

- Any course of oral/systemic corticosteroids started within 7 days of finishing a previous course will be considered as treatment for a single exacerbation
- Any course of antibiotics started within 7 days of finishing a previous course will be considered as treatment for a single exacerbation

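### A temporary stop of study drug for an exacerbation has no route of its own: Section 12.9.5 permits it, but Sections 8.1 and 8.1.7 and SoA footnote 10 provide only for leaving the treatment period

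*Protocol*

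**What the plan says.** Section 12.9.5 (Appendix 9) covers the index exacerbation and any later one, in every study period. Where medically necessary, qualified staff may stop "double-blind study treatment temporarily in order to treat the COPD exacerbation". The adverb implies a return to drug. The section does not say when or how, or which visits the participant then attends.

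Section 8.1.7 is headed Temporary Discontinuation. Its only sentence begins: "A participant may be withdrawn from study treatment as discussed in Section 8.1 but continue in the follow-up period of the study". It mentions neither a pause nor a return to treatment.

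Section 8.1, to which it refers, is mandatory in tone: "Participants who discontinue from study treatment will move directly into the 12-Week Post Treatment Follow Up Period starting with Visit 7", 28 days after the discontinuation date. Footnote 10 of the follow-up SoA repeats the move to Visit 7, and the Synopsis has the same rule. None makes an exception for a temporary stop.

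Three other places touch the question without settling it:

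- Section 8.1.8.1: "Study treatment restart or rechallenge after liver chemistry stopping criteria are met by any participant in this study is not allowed". It is silent on restart after any other kind of stop.
- Section 8.2: "Treatment failure or recurrent exacerbation does not mandate withdrawal from the study, unless there is a safety concern". This concerns the study, not the drug.
- Section 7.6.1: "Treatment start and stop dates, including dates for treatment delays will also be recorded in the eCRF". Dosing gaps are foreseen, but no visit schedule is attached to them.

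**The concern.** A site that looks up the section named for a temporary stop is sent to post-treatment follow-up. A site that reads Appendix 9 can pause, resume and carry on with the treatment-period visits. Both could say that they followed the protocol.

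The trigger makes this a statistical matter. The key secondary endpoint is the "number of exacerbations (moderate and severe) over the 12-Week treatment period", and the event that permits a temporary stop is an exacerbation. Whether a participant still has an on-treatment Day 84 FEV1, and whether later events fall inside the treatment period, may then depend on having had an outcome event and on how the site read the text. If the drug lowers the exacerbation rate, the number exposed to the ambiguity also differs by arm. Visits that were never held cannot be recovered at the analysis stage.

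**Working it through.** **Step 1: the two routes.** Take a participant whose drug is stopped for an exacerbation on Day 30 (an illustrative day).

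- Route A, Section 12.9.5 with resumption: Visits 5 and 6 follow on Days 56 and 84. The Day 84 FEV1 is on treatment.
- Route B, Section 8.1.7 read with 8.1: Visits 7, 8 and 9 fall at 30 + 28 = Day 58, 30 + 56 = Day 86 and 30 + 84 = Day 114, all off drug. The FEV1 nearest Day 84 is taken 86 - 30 = 56 days after the stop.

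This uses the 28-day interval of Section 8.1. Footnote 10 states the interval in weeks, which needs reconciling as well.

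**Step 2: reproduce the protocol's figure.** Section 10.1.2 gives a placebo rate of 0.51 per 12 weeks, dispersion k = 3.5, 340 per arm, a true reduction of 25% (so 0.51 x 0.75 = 0.3825 on drug), and success if the posterior probability exceeds 80%. It states a 76% chance of success.

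- SE^2 = (1/0.51 + 1/0.3825 + 2 x 3.5)/340 = (1.961 + 2.614 + 7)/340 = 0.0340, so SE = 0.1845.
- Probability = Phi(|ln 0.75|/SE - z(0.80)) = Phi(0.2877/0.1845 - 0.8416) = 76.3%.

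The stated 76% reproduces, so these inputs are used as the protocol means them.

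**Step 3: how many have the triggering event.** For a negative binomial count with mean m over a full 12 weeks, P(at least one) = 1 - (1 + k m)^(-1/k).

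- Placebo, k = 3.5: 1 - 2.785^(-1/3.5) = 0.254, or 86 of 340.
- 750 mcg, k = 3.5: 1 - 2.339^(-1/3.5) = 0.216, or 73 of 340.
- k = 2 (also in the protocol's Table 5): 0.296 and 0.247, or 101 and 84.
- k = 1 (also in Table 5): 0.338 and 0.277, or 115 and 94.

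**Step 4: from events to pauses.** The protocol gives no share s of these participants whose drug would be paused. The affected numbers are 86s and 73s. With s as a pure assumption:

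- s = 20%: about 17 and 15.
- s = 50%: about 43 and 37.
- s = 100%: 86 and 73, a difference of 13 of 340, or 3.8%.

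Only those handled by Route B lose treatment-period visits, so the true loss is smaller than any of these lines.

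**The case against.** The strongest reply is that the texts can be read together. Section 8.1.7 is permissive and forbids no pause. Section 12.9.5 is a specific permission. Section 8.1 governs those who discontinue, and a temporary stop need not count as discontinuation. Section 8.1.8.1 bars restart only after liver events, which suggests it is open otherwise, and Appendix 7 uses a separate term for permanent stopping. Section 7.6.1 expects delays and requires contact with the sponsor or monitor when drug is prematurely discontinued.

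Much of this stands. A reader might infer a flat prohibition in one place and a permission in another; the documents do not support that. What remains is that Section 8.1 never separates a pause from a permanent stop, Appendix 7 does so only for liver events, and the section whose heading promises a rule for pauses leads out of the treatment period.

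Other stronger readings also fail:

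- **That later exacerbations are lost.** Section 12.9.4 collects them until Visit 9, and the model in Section 10.3.1 has an offset for time in study. They are recorded, but after treatment has ended.
- **That all FEV1 information near Day 84 is lost.** With 28-day spacing, a stop by about Day 70 still gives a measurement within 14 days of Day 84 (70 + 28 = 98). What is lost is the on-treatment value.
- **That Section 9.3 is a further conflict.** Its mention of dose interruptions concerns overdose only.
- **That exposure is not comparable between sites.** Randomization is central and the comparison is between arms, so differing site practice does not by itself undermine it.
- **That a known fraction is paused.** No share is stated anywhere.

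**Conclusion.** The inconsistency is real and no other section resolves it. For a temporary stop after an exacerbation the protocol supports two different visit schedules, and one of them forgoes the on-treatment Day 84 FEV1 and shortens the treatment period.

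On the protocol's own inputs, about 86 placebo and 73 nemiralisib 750 mcg participants of 340 each have a subsequent moderate or severe event. The figures assume a full 12 weeks of follow-up, dispersion 3.5 and a true 25% reduction; with dispersion 1 they are 115 and 94. They are upper bounds for subsequent moderate or severe events. They do not count pauses for the index exacerbation, which every participant has and which Section 12.9.5 also covers.

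The documents do not show a material bias between arms. The pause share and the split between routes are both unknown, and even with every such participant paused the arms differ by about 13 of 340. The case for acting is that the loss is avoidable, falls on the primary endpoint, is triggered by an outcome event, and costs little to prevent.

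**What to change.** The sponsor should reconcile Sections 8.1, 8.1.7 and 12.9.5 and SoA footnote 10. Whether a pause with resumption is allowed is for its clinical team to decide; this review takes no position.

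If it is allowed, add for data collection:

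- The move to Visit 7 follows only a stop recorded as permanent.
- Participants who resume keep the Visit 3-6 schedule.
- Pause and restart dates go in the eCRF, which Section 7.6.1 already foresees by collecting treatment delay dates.

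If it is not allowed, Section 12.9.5 and the heading of 8.1.7 should be brought into line with that decision.

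The cost is wording in four places and a memo to sites, with no new procedure. If pauses are allowed, some participants will have an exposure gap inside the treatment period, which the recorded dates would make visible to the analysis.

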8.1.8. Rechallenge

8.1.8.1. Study Treatment Restart or Rechallenge

Study treatment restart or rechallenge after liver chemistry stopping criteria are met by any participant in this study is not allowed.

8.2. Withdrawal from the Study

A participant may withdraw from the study at any time during the study (including the Screening Period, the 12-Week Double-Blind Treatment Period or the 12-Week Post-Treatment Follow-Up Period) at his/her own request, or may be withdrawn at any time at the discretion of the investigator for safety, behavioral, compliance or administrative reasons.

If a higher than expected number of participants prematurely discontinues double-blind study treatment or prematurely discontinues from the study, additional participants may be randomized, at the discretion of the Sponsor.

If the participant withdraws consent for disclosure of future information, the sponsor may retain and continue to use any data collected before such a withdrawal of consent.

If a participant withdraws from the study, he/she may request destruction of any samples taken and not tested, and the investigator must document this in the site study records.

Refer to the SoA (Section 2) for data to be collected at the time of study withdrawal and follow-up and for any further evaluations that need to be completed.

Treatment failure or recurrent exacerbation does not mandate withdrawal from the study, unless there is a safety concern as judged by the Investigator, in consultation with the Medical Monitor if necessary.

The primary reason for subject withdrawal will be recorded in the eCRF. Primary reasons for withdrawal will be categorized as:

- adverse event
- withdrew consent
- lost to follow-up
- protocol deviation
- lack of efficacy
- subject reached protocol-defined stopping criteria
- study closed/terminated
- investigator discretion

Specific regard should be given to distinguishing withdrawals due to an adverse event, lack of efficacy and protocol deviation. Participant compliance with study treatment during the 12-Week Double-Blind Treatment Period will be assessed as described in Section 7.6.1.

8.3. Lost to Follow Up

A participant will be considered lost to follow-up if he or she repeatedly fails to return for scheduled visits and is unable to be contacted by the study site.

The following actions must be taken if a participant fails to return to the clinic for a required study visit:

- The site must attempt to contact the participant and reschedule the missed visit as soon as possible and counsel the participant on the importance of maintaining

the assigned visit schedule and ascertain whether or not the participant wishes to and/or should continue in the study.

- Before a participant is deemed lost to follow up, the investigator or designee must make every effort to regain contact with the participant (where possible, 3 telephone calls and, if necessary, a certified letter to the participant's last known mailing address or local equivalent methods). These contact attempts should be documented in the participant's medical record.
- Should the participant continue to be unreachable, he/she will be considered to have withdrawn from the study with a primary reason of lost to follow-up.

9. STUDY ASSESSMENTS AND PROCEDURES

- Study procedures and their timing are summarized in the SoA (Section 2).
- Protocol waivers or exemptions are not allowed.
- Immediate safety concerns should be discussed with the Medical Monitor immediately upon occurrence or awareness to determine if the participant should continue or discontinue study treatment.
- Adherence to the study design requirements, including those specified in the SoA (Section 2), is essential and required for study conduct.
- All screening evaluations must be completed and reviewed to confirm that potential participants meet all eligibility criteria. The investigator will maintain a screening log to record details of all participants screened and to confirm eligibility or record reasons for screening failure, as applicable.
- Procedures conducted as part of the participant's routine clinical management (eg, blood count) and obtained before signing of ICF may be utilized for screening or baseline purposes provided the procedure met the protocol-specified criteria and was performed within the time frame defined in the SoA (Section 2).

The maximum amount of blood collected from each participant over the duration of the study, including any extra assessments that may be required, will not exceed the following:

- Males:
 - Main Study: approximately 189 mL (including blood samples for genetic research and biomarkers)
 - PK Sub-group: approximately 199 mL (including the above bullet and the serial PK samples)
- Females
 - Main Study: approximately 214 mL (including blood samples for pregnancy testing, genetic research, and biomarkers)
 - PK Sub-group: approximately 224 mL (including the above bullet and the serial PK samples)

Repeat or unscheduled blood samples may be taken for safety reasons or for technical issues with the samples.

The following procedures must be completed to ensure that the participant is eligible for the study:

- Obtain informed written consent
- Review inclusion/exclusion criteria, including concomitant medications.
- Full source documentation for the above qualifying procedures and related results are required.
- Any protocol-specified study qualification procedures not already done as part of routine care will need to be conducted after the participant signs the ICF and before randomization.
- The results of all study qualification procedures, whether performed as part of routine care or as a study-specific procedure, are required to assess participant inclusion/exclusion criteria and should, if possible, be available prior to randomization.
- For prompt assessment of the participant's eligibility local laboratory samples should be taken at Screening and the results received and reviewed prior to randomisation to allow review of exclusion criteria 18. It is important that a sample for analysis by the central laboratory is obtained at the same time and promptly sent to the central laboratory. The local lab results will not be entered into the CRF; however, they will be filed in the respective participant's source documentation.
- Samples for Hepatitis B surface antigen, Hepatitis C virus antibody, and HIV antibody will be submitted to the central laboratory **only** for analysis and do not need to be submitted to the local laboratory. Participants who are otherwise eligible may be randomized prior to the receipt and review of these results. If the result for one or more of these parameters is positive, then the participant will need to be withdrawn from the study. Therefore, it is important that a detailed medical history is performed at Screening (Visit 1), in order to minimize the potential for randomization of participants who are positive for one or more of these parameters.
- Those samples taken prior to or at the time of randomization and sent to the central laboratory will serve as the baseline for assessment of potential treatment effect (see the Schedule of Activities in Section 2).
- The screening process ends when randomization occurs. Randomization and first dose of the double-blind study treatment administration should take place as soon as possible following diagnosis of acute moderate/severe exacerbation of COPD and completion of the EXACT-PRO questionnaire and FEV₁ measurement and no later than 48hrs after start of SoC.

